### **6.3 Laboratory Test Abnormalities**

The following laboratory abnormalities should be captured as appropriate:

- Any laboratory test result that is clinically significant or meets the definition of an SAE
- Any laboratory abnormality that required the subject to have study drug discontinued or interrupted
- Any laboratory abnormality that required the subject to receive specific corrective therapy.

It is expected that wherever possible, the clinical, rather than the laboratory term would be used by the reporting investigator (eg, anemia versus low hemoglobin value).

### **6.4 Pregnancy**

If, following initiation of the investigational product, it is subsequently discovered that a study subject or a female partner of a male study participant is pregnant or may have been pregnant at the time of investigational product exposure, including during at least 6 half-lives after product administration, the investigational product will be permanently discontinued for the female study participant in an appropriate manner (eg, dose tapering if necessary for subject safety). Protocol-required procedures for study discontinuation and follow-up must be performed on the subject unless contraindicated by pregnancy (eg, x-ray studies). Other appropriate pregnancy follow-up procedures should be considered if indicated. Follow-up information regarding the course of the pregnancy, including perinatal and neonatal outcome and, where applicable, offspring information must be reported. Any pregnancy that occurs in a female partner of a male study participant should be reported to the IRB.

### **6.5 Overdose**

An overdose is defined as the accidental or intentional administration of any dose of a product that is considered both excessive and medically important. All occurrences of overdose must be reported as SAEs (see Section 6.1.1 for reporting details).

### **6.6 Other Safety Considerations**

Any significant worsening noted during interim or final physical examinations, electrocardiograms, x-rays, and any other potential safety assessments, whether or not these procedures are required by the protocol, should also be recorded as a nonserious or serious AE, as appropriate, and reported accordingly.

## 7 DATA MONITORING COMMITTEE

To provide independent oversight for safety, study conduct and risk-benefit-ratio, an independent DMC made up of Moffitt faculty from the SPORE IAC and a patient advocate will provide oversight to this combination study of panobinostat with ipilimumab in subjects with melanoma. This committee will strictly serve in an advisory capacity to the study team. The committee will periodically review aggregate data from the study, specifically review all cases of Grade 3 or greater irAEs and will advise the study team regarding subject management, continuation, modification or discontinuation of dose regimens as appropriate. A charter detailing the activities of this DMC is available.

## 8 STATISTICAL CONSIDERATIONS

### 8.1 Sample Size Determination

Dose Escalation: This is a Phase I dose escalation trial and the sample size at each dose depends on the observed toxicity; however a total of 36 subjects for the dose-escalation study allows sufficient number of subjects if needed, e.g. more than 6 subjects if dose-limiting toxicities are observed among 2 of 6 subjects, to better estimate the toxicity rates per dose, and more accurately determine the MTD. Cohorts of 3 subjects with expansions to 6, or possibly even 9 or 12 subjects will be treated at each suggested dose level until MTD is determined.

In this protocol, we will be using a new phase I trial approach (Table 8.1), modified from a design from Ji et al. This approach provides a broader phase I experience than the traditional 3+3 design, thus allowing for a more robust choice of an MTD. While setting the target toxicity rate at 18%, this design allows further examination of a dose when 2 DLTs occur among 6 patients, while still keeping the observed toxicity at the MTD well managed (it is below 26% for sample sizes  $\geq 9$ ). The trials will enroll up to 36 patients for determination of the MTD, but will be successfully concluded earlier if 12 patients are accrued at the dose determined to be the MTD, with 3 DLTs. If, at any time, one de-escalates to a dose which has already accrued 12 patients, the study will be terminated and that dose declared to be the MTD. The MTD is obtained at 33 patients if 9 or 12 patients have been accrued at the current dose and the dose is acceptable (E, S or C). Otherwise, if the current dose has  $\leq 1$  of 3, or  $\leq 2$  of 6 DLTs, then three more patients will be accrued at that dose – if at most 1 of 6, or 2 of 9 have DLTs, that dose is the MTD.

**Table 8.1 Decision Rules on dose escalation based on number of DLTs\*\***

N*	Observed DLTs per cohort and treatment decisions									
	0	1	2	3	4	5	6			
3	E	S	DU	DU	-	-	-	-	-	-
6	E	E	S	DU	DU	DU	DU			
9	E	E	S	D	DU	DU	DU			
12	E	E	E	C	DU	DU	DU			

N\* =number of subjects treated at a given dose level

S: stay at the same dose and enroll a cohort of 3 more subjects at that dose

E: escalate to the next higher dose by enrolling 3 more subjects

D: de-escalate to the lower dose, and enroll 3 more subjects at the lower dose, or  
DU: declare the current dose as unacceptable and unsafe, de-escalate to the lower dose, and enroll 3 more subjects at the lower dose

C: Study completed and dose is declared to be the MTD

\*\*for MTD target toxicity pT=18%, and allowing any dose with pT in (17%, 19%) to be selected

The modifications involve escalating the dose whenever the observed toxicity rate is below 17% and using the N-1st patient to define the change when the toxicity rate exceeds 19% and  $N \geq 9$  to account for the fact that the design is being used in cohorts of 3 rather than continuously as designed by Ji et al.

## 8.2 Endpoint Definitions

### 8.2.1 Safety Endpoints

All subjects who receive study any drug therapy will be evaluated for safety. Safety assessments will be based on medical review of adverse event reports and the results of vital sign measurements, physical examinations, and clinical laboratory tests. Triplicate 12-lead electrocardiograms (ECGs) will be collected prior to dosing on Day 1 of induction cycle 1. Single 12-lead ECGs will be collected at screening, prior to dosing on Day 1 of each treatment cycle and at the end of treatment visit.

Adverse events will be categorized using the most current version of MedDRA and adverse events and laboratory tests will be graded using National Cancer Institute (NCI) Common Terminology Criteria for Adverse Events (CTCAE) v4.0. Immune-related adverse experiences (irAEs) among treated subjects will be specifically assessed as well.

### 8.2.2 Efficacy Endpoints

#### 8.2.2.1 Efficacy Endpoints based on RECIST 1.1

The best overall response (BOR), computed for all treated subjects, is defined as the best response designation over the study as a whole, recorded between the dates of first dose until the last tumor assessment prior to subsequent therapy.

**Objective Response Rate (ORR)** is defined as the total number of subjects whose best response outcome is a complete response (CR) or partial response (PR) divided by the total number of evaluable subjects.

**Disease Control Rate (DCR)** is defined as the total number of subjects whose best response outcome is a complete response (CR) or partial response (PR), or stable disease divided by the total number of evaluable subjects.

**Prolonged Disease Control Rate (PDCR)** is defined as the total number of subjects whose best response outcome is a complete response (CR) or partial response (PR), or stable disease lasting at least 12 weeks, divided by the total number of evaluable subjects.

**Progression Free Survival (PFS):** is defined for each subject as the time from first dosing to the first observation of disease progression or death due to any cause. If a subject has not progressed or died at the time of analysis, PFS will be censored on the date of the last disease assessment. Subjects who do not have any tumor assessment on treatment will be censored on the day of the first dose.

**Duration of Overall Response:** will be computed for all subjects whose best response is either a PR or CR and is calculated from the time the measurement criteria are met for PR or CR, whichever is recorded first, until the date of documented progressive disease or death.

**Duration of Disease Control:** will be computed for the subjects who had BOR outcome of CR, PR, or Stable Disease and is calculated from the beginning of treatment until the time of documented disease progression.

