- **Safety Outcome Measures:** All subjects who receive study drug therapy will be evaluated for safety. Safety assessments will be based on medical review of adverse event reports and the results of vital sign measurements, physical examinations, and clinical laboratory tests. Triplicate 12-lead electrocardiograms (ECGs) will be collected prior to dosing on Day 1 of induction cycle 1. Single 12-lead ECGs will be collected at screening, prior to dosing on Day 1 of all treatment cycles (with the exception of induction cycle 1 as above) and at the end of treatment.

Adverse events will be categorized using the most current version of MedDRA and adverse events and laboratory tests will be graded using National Cancer Institute (NCI) Common Terminology Criteria for Adverse Events (CTCAE) v4.0. Hepatic adverse events (AST, ALT, T Bili) will also be recorded relative to ULN. Immune-related adverse experiences (irAEs) among treated subjects will be specifically assessed as well.

- **Efficacy Measures:** Tumor response will be determined for all subjects by RECIST 1.1 (see Appendix 3) as well as by immune-related response criteria (irRC; see Appendix 4). RECIST 1.1 will be used for statistical analysis of efficacy in this study. Treatment decisions related to subject management may be based on the irRC criteria, but for the purposes of reporting efficacy RECIST 1.1 criteria will be used. Assessments of tumor status will be made during screening, then at 6 weeks and 12 weeks, and subsequently every 12 weeks. Tumor assessments at the end-of-treatment (EOT) or 90-day follow-up visit will be performed only if not assessed within the prior 12 weeks. Individual subject's best overall response (BOR) will be assessed, and progression free survival (PFS) will be calculated by RECIST 1.1 response criteria. Other endpoints are Objective response (OR) defined as BOR outcome of CR or PR for RECIST 1.1, disease control (DC) defined as BOR outcome of CR, PR, or Stable Disease by RECIST 1.1. Duration of response and duration of disease control will also be calculated.

Statistical Methods:

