#### **1.4.5 Rationale for use of Immune-related Response Criteria (irRC) to Guide Clinical Care and Assessment of Clinical Activity**

In prior ipilimumab clinical studies, particularly those in metastatic melanoma, clinical efficacy appears to be characterized by objective tumor response (CR and PR), durable stable disease (commonly lasting 6 or more months in subjects receiving 10 mg/kg ipilimumab), and stable disease evolving to objective response after more than a year of follow-up in the absence of alternative anti-cancer therapy. In addition, melanoma subjects receiving ipilimumab who are found to have new lesions at the first follow-up tumor assessment and who are therefore scored as progressors by the mWHO or RECIST criteria have been observed to have stable or decreasing tumor burden in spite of the presence of new lesions. Subjects with such “mixed responses” have been reported to go on to continued reduction in tumor burden in the absence of alternative anti-cancer therapy and objective tumor response by any measure.

The irRC were developed to provide a guide for clinical care of subjects on immunotherapy. Subjects with stable (irSD) or significantly decreasing (irPR) tumor burden despite the presence of new lesions remain on study and continue to receive study drug. Subjects with increasing tumor burden (irPD) are declared progressors and taken off study drug. To account for the various spectra of patterns of new lesions, measurable new lesions are added to the calculation of tumor burden (e.g. added to the SPD of the index lesions). Thus, subjects with many large new lesions will be scored as irPD even if the index lesions are stable or decreasing.

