#### **4.3.4 Duration of Treatment**

Subjects may remain on study therapy until progressive disease as determined by immune-related response criteria (irRC), withdrawal due to toxicity, withdrawal of consent, or at the discretion of the investigator.

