**5.4 Efficacy Assessments**

In this study, immune-related Response Criteria (irRC; see Appendix 4) will be used to assess subject response to study treatment and guide clinical care. However, response- based assessments in this study will be captured using both modified irRC and RECIST 1.1. The investigator will determine the irRC response at each tumor assessment. The RECIST 1.1 response for the patient will be calculated from the tumor assessment data by the Sponsor and will be used for reporting purposes. The RECIST 1.1 criteria will be used to determine subjects’ best overall response (BOR), and for statistical analysis of efficacy in this study. Assessments of tumor status will be made during screening and then at 6 and 12 weeks and then every 12 weeks thereafter. The irRC represent modifications of the modified WHO criteria reflecting the clinical experience with ipilimumab in the completed and/or ongoing clinical studies in which objective and durable responses (as per mWHO) were observed in subjects following progression and without intervening alternative anti-cancer therapy. As such, the irRC are designed to capture clinical activity of ipilimumab immunotherapy that may not be adequately addressed by the RECIST 1.1 criteria and will only be used for patient management decisions, not formal efficacy reporting.

[REDACTED]

[REDACTED]

[REDACTED]

[REDACTED]

[REDACTED]

[REDACTED]

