**8.2.2.2 Efficacy Endpoints based on Immune Related Criteria (irCR)**

**Immune Related Best Overall Response (irBOR)** is the best irRC designation over the study as a whole, recorded between the date of first dose until the last tumor assessment prior to subsequent therapy (except for local palliative radiotherapy for painful bone lesions) for the individual subject in the study. irCR or irPR determinations included in the irBOR assessment must be confirmed by a second (confirmatory) evaluation meeting the criteria for response and performed no less than 4 weeks after the criteria for response are first met.

**Immune-related Response Rate (irRR)** is defined as the proportion of response evaluable subjects whose irBOR outcome is irPR, irCR.

**Immune-related Disease Control Rate (irDCR)** is defined as the proportion of the response evaluable subjects whose irBOR outcome is irPR, irCR, or irSD.

**Immune-related Prolonged Disease Control Rate (irPDCR)** is defined as the proportion of the response evaluable subjects whose irBOR outcome is irPR, irCR, or irSD, with stable disease lasting at least 12 weeks.

**Immune-related Progression-Free Survival (irPFS)** is defined as the time between the first dosing date and the date of irPD or death, whichever occurs first. For subjects with no recorded post-baseline tumor assessment, irPFS will be censored at the day of first dose. A subject who dies without reported irPD will be considered to have progressed on the date of death. For those who remain alive and have no irPD, irPFS will be censored on the date of last evaluable tumor assessment. Subjects who do not have any tumor assessment on treatment will be censored on the day of the first dose.

**Duration of Immune Related Overall Response:** will be computed for all subjects whose irBOR outcome is either an irPR or irCR and is calculated from the time the measurement criteria are met for irPR or irCR, whichever is recorded first, until the date of documented progressive disease or death by irRC.

**Duration of Immune Related Disease Control:** will be computed for the subjects who had irBOR outcome of irCR, irPR, or ir Stable Disease and is calculated from the beginning of treatment until the time of documented disease progression by irRC.

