### **Evaluation of best overall response**

The best overall response is the best response recorded from the start of the treatment until disease progression/recurrence (taking as reference for PD the smallest measurements recorded since the treatment started). In general, the patient's best response assignment will depend of the achievement of both measurements and confirmation criteria.

Patients with a global deterioration of health status requiring discontinuation of treatment without objective evidence of disease progression at that time should be classified as having "symptomatic deterioration". Every effort should be made to document the objective progression even after discontinuation of treatment.

- In some circumstances it may be difficult to distinguish residual disease from normal tissue. When the evaluation of complete response depends on this determination, it is recommended that the residual lesion be investigated (fine needle aspirate/biopsy) to confirm the complete response status.

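### RECIST best overall response has two conflicting windows (Section 8.2.2.1 and Appendix 3), and irPFS gives two outcomes for a death before any scan; only secondary efficacy is affected

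*Combined protocol and SAP*

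**What the plan says.** **RECIST BOR.** Section 8.2.2.1 gives this definition: "best response designation over the study as a whole, recorded between the dates of first dose until the last tumor assessment prior to subsequent therapy". Progression does not close that window. Appendix 3 (Evaluation of best overall response) says: "The best overall response is the best response recorded from the start of the treatment until disease progression/recurrence". The Synopsis (Efficacy Measures) makes Appendix 3 operative: "Tumor response will be determined for all subjects by RECIST 1.1 (see Appendix 3".

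**irBOR.** Section 8.2.2.2 uses almost the same window as Section 8.2.2.1: irBOR "is the best irRC designation over the study as a whole, recorded between the date of first dose until the last tumor assessment" before subsequent therapy, with an exception for local palliative radiotherapy. Yet Section 5.4 says that the irRC "will only be used for patient management decisions, not formal efficacy reporting", and assigns BOR and the efficacy statistics to RECIST 1.1.

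**Treatment after RECIST progression.** Section 4.3.4: "Subjects may remain on study therapy until progressive disease as determined by immune-related response criteria (irRC". Section 1.4.5 describes ipilimumab subjects with new lesions who, though "scored as progressors by the mWHO or RECIST criteria have been observed to have stable or decreasing tumor burden", "have been reported to go on to continued reduction in tumor burden in the absence of alternative anti-cancer therapy and objective tumor response". Appendix 4 (4.1) likewise notes that responses can follow conventional progression.

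**PFS and irPFS.** Both count death as an event. The irPFS paragraph in Section 8.2.2.2 states first-dose censoring for subjects without a tumor assessment twice, once for no post-baseline assessment and once for none on treatment. It also dates progression at death for anyone who dies without reported irPD. The PFS paragraph in Section 8.2.2.1 ends with one such no-scan sentence.

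**Durations.** Under both criteria, duration of response ends at progression or death, and duration of disease control ends at documented progression only. No duration endpoint has a stated censoring date. Section 8.3.2 plans Kaplan-Meier estimates for them.

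**The concern.** The first problem is a conflict over the reported endpoint. RECIST BOR feeds ORR, DCR and prolonged DCR. Two analysts who follow different parts of the same document could classify a subject who regresses after RECIST progression as a responder or as a progressor. The design makes such subjects foreseeable, because treatment and scanning can go on between RECIST progression and irPD.

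The second problem is a missing order of precedence. A subject who dies before the week-6 scan satisfies both the first-dose censoring rule and the death rule for irPFS. Censoring such a subject at day 0 removes an early failure from the curve. irPFS also enters the planned analyses of absolute lymphocyte count slope (Section 8.3.4).

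In both cases the more favourable reading is open to be chosen after the data are seen, in groups as small as 12.

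**Working it through.** The plan attaches no figure to these definitions, so there is nothing to reproduce. The counts below are assumed. The group sizes come from Section 8.1: 12 subjects at the MTD and up to 36 in all.

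**1. One subject under the two BOR windows.** Scans are at weeks 6 and 12 and then every 12 weeks (Section 5.4). Appendix 3 requires confirmation of a response at least 4 weeks later. Suppose RECIST PD at week 6, treatment continued under irRC, PR criteria met at week 12 and confirmed at week 24, and no subsequent therapy.

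| Endpoint | Appendix 3 window | Section 8.2.2.1 window |
|---|---|---|
| PFS | event, week 6 | event, week 6 |
| BOR | PD | PR |
| Counts in ORR | no | yes |
| Duration of response | not applicable | starts week 12, after the PD |
| Duration of disease control | not applicable | ends week 6, before the response |

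The right-hand column does not hang together, which points to the Appendix 3 window as the workable one.

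**2. Effect on ORR.** Each added responder moves ORR by 1/n: 1/12 = 8.3 points, 1/36 = 2.8 points. The 90% Clopper-Pearson limits (the Synopsis method) are the 5% quantile of Beta(x, n−x+1) and the 95% quantile of Beta(x+1, n−x).

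| Responders | ORR | 90% CI |
|---|---|---|
| 2/12 | 16.7% | 3.0 to 43.8 |
| 3/12 (one added) | 25.0% | 7.2 to 52.7 |
| 4/12 (two added) | 33.3% | 12.3 to 60.9 |
| 6/36 | 16.7% | 7.5 to 30.3 |
| 7/36 (one added) | 19.4% | 9.5 to 33.4 |

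**3. DCR and prolonged DCR.** A subject with SD, PR or CR before the PD is already in DCR under either window. DCR therefore rises only if no SD or response came first, as in the week-6 PD above. Prolonged DCR rises only if there was no earlier response and no SD of the required length (12 weeks in Section 8.2.2.1).

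**4. irPFS.** Let k of n subjects die before any scan, with no other censoring up to time t, and let m be alive and free of irPD at t.

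- Deaths as events: S(t) = m/n.
- Deaths censored at day 0: S(t) = m/(n−k).
- Ratio: n/(n−k). At n=12 this is 12/11 = 1.09 for one death and 12/10 = 1.20 for two. At n=36 with one death it is 36/35 = 1.03.

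For example, 3/12 = 25.0% becomes 3/11 = 27.3% or 3/10 = 30.0%.

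The median, taken as the first time S is at or below 0.5, moves only if the curve is near 50% at a scan. With one early death:

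- 6/12 = 50.0% at week 6 and 3/12 at week 12: censoring gives 6/11 = 54.5% and 27.3%, so the median moves from week 6 to week 12.
- 7/12 = 58.3% at week 6 and 4/12 = 33.3% at week 12: censoring gives 7/11 = 63.6% and 4/11 = 36.4%, so the median is week 12 either way.

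**The case against.** **The BOR texts can be reconciled.** The Section 8.2.2.1 definition sits under a RECIST 1.1 heading, the Synopsis sends RECIST to Appendix 3, and the subsequent-therapy cutoff could be an additional limit. Section 1.4.2.3 describes late regressions as additional to RECIST response, and Section 5.4 says that the irRC exist to capture what RECIST may miss. This is probably what was intended, and where a new lesion persists RECIST would not readily give a PR. But no sentence says that the earlier cutoff applies. The only rule in Appendix 3 that bars a response after progression is the window that Section 8.2.2.1 contradicts.

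**Censoring rules ordinarily apply to subjects without an event.** For RECIST PFS that reading is available, since the no-scan sentence follows the rule for subjects who have neither progressed nor died. For irPFS it is harder to sustain: the no-scan rule appears twice, never limited to living subjects, next to an unqualified death rule.

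**Stronger readings that a reader might infer.** One is that the literal BOR window raises DCR and prolonged DCR whenever it raises ORR; step 3 shows that it does not. Another is that leaving death out of disease-control duration is an error. It is not: ending at documented progression is a coherent time-to-progression quantity, and adding death would change what is estimated. The absent censoring dates for durations are missing detail, not a contradiction.

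**The stakes are limited.** This stands. Efficacy is secondary and descriptive, BOR and PFS are listed per subject, the sponsor derives RECIST response at a single-site study, and sensitivity analyses are allowed. The intervals in step 2 overlap heavily, and no decision rule uses ORR.

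**Conclusion.** The plan is wrong as written on two definitions, both confined to secondary efficacy. The RECIST BOR window in Section 8.2.2.1 contradicts Appendix 3, and followed literally can count a post-progression regression as a RECIST response. The irPFS definition assigns two outcomes to a death before any post-baseline scan; RECIST PFS shares the ambiguity only on a literal reading.

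The size is 8.3 ORR points per affected subject at n=12 and 2.8 at n=36. For irPFS it is a factor of 1.09 per single early death at n=12, with a change in the median only if the curve lies near 50% at a scan. These figures rest on assumed counts, and the irPFS factor also assumes no other early censoring. The documents do not support any estimate of how often either case will arise, nor a claim that the efficacy conclusions would be reversed. The DLT-based MTD rule does not use these endpoints. Correction is advisable before analysis, but this does not threaten the primary objective.

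**What to change.** 1. **Section 8.2.2.1, BOR:** define RECIST BOR from first dose to first RECIST progression or start of subsequent therapy, whichever comes first, and cite Appendix 3. Leave later regressions to irBOR.
2. **Sections 8.2.2.1 and 8.2.2.2, PFS and irPFS:** limit first-dose censoring to subjects who are alive with no post-baseline assessment, and count every death without prior progression as an event on the date of death. State the irPFS no-scan rule once.
3. **Minor clarifications:** say how a death without progression is handled in duration of disease control (as an event or censored), and give a censoring date for all duration endpoints, for example the last tumor assessment for subjects alive without progression.

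The cost is wording and programming only. No visit, sample size or dose-escalation rule changes. Reported efficacy may look slightly less favourable than under the literal text.
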